5.4.2 NASAL ALLERGEN CHALLENGE (NAC)

The NAC will be performed using grass pollen extract (*Phleum pratense*) (ALK-Abelló). Application of the allergen to the nasal mucosa is undertaken using a disposable nasal pump spray (Bidose®; Aptar Pharma, France). Nasal challenge provokes immediate symptoms at 0-1 hour after challenge followed by milder delayed-in-time late responses at 1-10 hours (generally mild and not captured in this study). The participant will experience typical hay fever symptoms including nasal itching, nasal blockage, sneezing, nasal watery discharge, itchy eyes, watery eyes, and redness of the conjunctivae. If bothersome nasal and/or ocular symptoms persist after the period of 0-1 hour observation in the clinical unit, participants will be offered treatment with oral antihistamines. Unless bothersome symptoms persist, the participants will be discharged after one hour and provided with a telephone contact number with immediate access for 24 hours after challenge.

There is a remote risk of provoking mild asthma symptoms after a NAC. All participants' peak expiratory flow (PEF) will be recorded before and after nasal challenge. Inhaled bronchodilators and corticosteroids will be immediately available for treatment. As for any intervention with allergen to which an individual is sensitive, there is the theoretical risk of developing a systemic allergic/anaphylactic reaction, although this has never been observed in studies of several hundred participants over the past 30 years in the Section for Allergy and Clinical Immunology at NHLI, Imperial College. Nevertheless, a trained physician and injectable adrenaline, oxygen and intravenous equipment and fluids will be immediately available in the clinical unit during participants' NAC visits.

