12.3.1.2 Selected Study Procedures

The study site will grade the severity of AEs for the following selected study procedures according to the following criteria:

Local Reactions:

- All local reactions to allergen skin testing and NACs that meet the definition of AEs (see Section 12.2.1) and are not associated with systemic signs or symptoms will be graded according to Table 8 and Table 9, respectively.

Systemic Reactions:

- All systemic reactions related to allergen skin testing or to the NAC procedure will be graded according to the WAO Subcutaneous Immunotherapy Systemic Reaction Grading System (see Appendix 14).
- The following modification will apply for NACs: Under Grade 1 (Symptoms/signs of 1 organ system present), "rhinitis (e.g., sneezing, rhinorrhea, nasal pruritus and/or

nasal congestion)” as well as “cough perceived to originate in the upper airway, not the lung, larynx or trachea” are not considered systemic reactions to NACs.

Table 8. Grading Table for Local Reactions to Allergen Skin Testing

Grade	Description
1	Bothersome, (interfering with usual daily activities or sleep).
2	Bothersome, requiring medication
3	Bothersome, requiring a visit to the study physician/emergency room for treatment

Table 9. Nasal Allergen Challenge (NAC) procedure (local reactions)

Grade	Description
1	Nasal or oropharyngeal symptoms requiring more than a single dose of an oral antihistamine and/or an intranasal decongestant spray as rescue medication.
2	Nasal or oropharyngeal moderate to severe symptoms interfering with usual daily activities not requiring oral steroids as rescue medication.
3	Severe nasal or oropharyngeal symptoms requiring oral or systemic steroids.
4	Life threatening and/or requiring hospitalization for upper airway obstruction or other local reaction reason

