APPENDIX 14. WAO SUBCUTANEOUS IMMUNOTHERAPY SYSTEMIC REACTION GRADING SYSTEM

World Allergy Organization Subcutaneous Immunotherapy Systemic Reaction Grading System (see text)				
Grade 1	Grade 2	Grade 3	Grade 4	Grade 5

Symptom(s)/ sign(s) of one organ system present¹
 
Cutaneous
 
Generalized pruritus, urticaria, flushing or sensation of heat or warmthⁱⁱ
 
or
 
Angioedema (not laryngeal, tongue or uvular)
 
or
 
Upper respiratory
 
Rhinitis (e.g., sneezing, rhinorrhea, nasal pruritus and/or nasal congestion)
 
or
 
Throat-clearing (itchy throat)
 
or
 
Cough perceived to come from the upper airway, not the lung, larynx, or trachea
 
or
 
Conjunctival
 
Conjunctival erythema, pruritus or tearing
 
Other
 
Nausea, metallic taste, or headache
	
Symptom(s)/ sign(s) of more than one organ system present
 
or
 
Lower respiratory
 
Asthma: cough, wheezing, shortness of breath (e.g., less than 40% PEF or FEV1 drop, responding to an inhaled bronchodilator)
 
or
 
Gastrointestinal
 
Abdominal cramps, vomiting, or diarrhea
 
or
 
Other
 
Uterine cramps
	
Lower respiratory
 
Asthma (e.g., 40% PEF or FEV1 drop, NOT responding to an inhaled bronchodilator)
 
or
 
Upper respiratory
 
Laryngeal, uvula or tongue edema with or without stridor
	
Lower or Upper respiratory
 
Respiratory failure with or without loss of consciousness
 
or
 
Cardiovascular
 
Hypotension with or without loss of consciousness
	
Death

Patients may also have a feeling of impending doom, especially in grades 2, 3, or 4.
 
Note: children with anaphylaxis seldom convey a sense of impending doom and their behavior changes may be a sign of anaphylaxis, e.g., becoming very quiet or irritable and cranky.

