10.3. Adverse Events

Adverse events for this study are defined as per the protocol section 12.2.1.

For purposes of analysis, treatment-emergent adverse events (TEAEs) will be defined as all reported AEs with a start date on or after the first date of study treatment.

In order to assign treatment-emergence status, partial or completely missing AE start dates will be imputed using the algorithm in [Appendix 15.3](#).

All AEs will be classified by system organ class (SOC) and preferred term (PT), according to Medical Dictionary for Regulatory Activities (MedDRA), version 23.1 or later.

The severity of AEs will be classified using various grading criteria depending on the type of AE as follows:

Type of AE	Name of Severity Grade Criteria	Grading Scale
All local reactions to SLIT	Grading Table for Local Reactions to SLIT	Grade 1, 2, 3, or 4
All local reactions to allergen skin testing	Grading Table for Local Reactions to Allergen Skin Testing	Grade 1, 2, or 3
All local reactions to the NAC procedure	NAC procedure (local reactions)	Grade 1, 2, 3, or 4
Any immediate (0-1hr) systemic allergic reaction that occurred following administration of either SLIT or dupilumab All systemic reactions related to allergen skin testing or to the NAC procedure	WAO Subcutaneous Immunotherapy Systemic Reaction Grading System	Grade 1, 2, 3, 4, or 5 (where 5 = death)

DAIT NIAID Immune Tolerance Network
Statistical Analysis Plan - ITN084AD GRADUATE

All local reactions to dupilumab All other AEs	National Cancer Institute's (NCI's) Common Toxicity Criteria for Adverse Events (CTCAE) v5.0	Grade 1, 2, 3, 4, or 5 (where 5 = death)
---	--	---

Note: See protocol section 12.3.1 for the definitions of each grading criteria.

Each AE is entered on the case report form (CRF) once at the highest severity. As such, no additional data manipulation is needed to identify events.

AE summaries during screening (i.e., any time pre-treatment for treated participants, or during screening period for non-treated participants) will be performed using the Screened sample. All other AE summaries will be performed for only treatment-emergent events by treatment arm using the Safety sample.

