An overall summary table will be created separately for 1.) during screening and 2.) only treatment-emergent events, to report the number of events and the number and percentage of participants having at least one event in the following categories. Categories with an asterisk (*) below are only relevant for the treatment-emergent summary (not during screening period).

- Any AE
- Any AE indicated as serious
- Any AE that led to study drug discontinuation*
- Any AE with an outcome of death
- Any AE that was reported as being related to any study drug*
 - Any AE that was reported as being related to SLIT
 - Any AE that was reported as being related to dupilumab
- Any AE that was reported as being related to any study procedure
 - Any AE that was reported as being related to skin prick test
 - Any AE that was reported as being related to NAC procedure
 - Any AE that was reported as being related to venipuncture
- AEs reported by maximum severity grade (all severity grade criteria combined)
- AEs reported by maximum severity grade (within each severity grade criteria separately)

For purposes of assigning relatedness to study drugs, “related” will be considered for analysis purposes if relationship entered on eCRF is “Possibly Related”, “Related”, or missing.

For purposes of assigning relatedness to study procedures, “related” will be considered for analysis purposes if relationship entered on eCRF is “Possibly Related” or “Related”. A missing category will be separately considered.

In addition, AEs classified by MedDRA SOC and PT will be summarized for each treatment group and overall, separately for 1.) during screening and 2.) only treatment-emergent events. These SOC/PT summaries will be repeated for each of the following categories:

- Any AE
- AEs by maximum severity (all severity grade criteria combined)
- AEs by maximum severity (within each severity grade criteria separately)
- SAEs by maximum severity (all severity grade criteria combined)
- SAEs by maximum severity (within each severity grade criteria separately)
- AEs by relationship to study drug (only applicable to treatment-emergent summary)
- AEs by relationship to study procedure (both screening and treatment-emergent summaries)

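### SAP 10.3 grades immediate systemic drug reactions and NAC or skin-test reactions on one WAO scale, no planned table isolates the WAO-graded drug-related reactions by arm, and the protocol is unclear on which scale grades NAC eye symptoms

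*SAP*

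**What the plan says.** **Grading and tabulation (SAP 10.3).** The WAO row of the severity table has two entries: "Any immediate (0-1hr) systemic allergic reaction that occurred following administration of either SLIT or dupilumab" and "All systemic reactions related to allergen skin testing or to the NAC procedure". The drug entry is limited to the hour after dosing; the procedure entry has no time limit.

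The overall summary then includes "AEs reported by maximum severity grade (within each severity grade criteria separately", so WAO is tabulated as one scale. The SOC and preferred-term displays also have a within-scale version. The displays by year repeat the overall summary, but by SOC and preferred term they give severity only with all scales combined.

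The same summary has lines for "Any AE that was reported as being related to SLIT" and "Any AE that was reported as being related to dupilumab", and for events related to the skin prick test, the NAC and venipuncture. Further SOC and preferred-term tables go by relationship to drug and to procedure. None is crossed with severity scale or grade.

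**Endpoint (Protocol 3.3, item 10).** The safety endpoint covers the number, severity and relatedness of both local and systemic events, summarized for each arm.

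**Eye symptoms after NAC.** Protocol 5.4.2 expects "itchy eyes, watery eyes, and redness of the conjunctivae", and 12.2.1 also lists eye symptoms as usual after a challenge. The exemption in 12.3.1.2 begins "The following modification will apply for NACs: Under Grade 1 (Symptoms/signs of 1 organ system present" and covers only rhinitis and upper-airway cough. Appendix 14 still lists "Conjunctival erythema, pruritus or tearing" under grade 1. Table 9, the local NAC scale, names only nasal or oropharyngeal symptoms in grades 1 to 3. Protocol 12.3.1.3 sends events not described in 12.3.1.1 or 12.3.1.2 to CTCAE.

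**The concern.** Two kinds of event with different meanings share one row. A systemic reaction to SLIT or dupilumab is a harm of treatment. A reaction to the challenge is provoked by the procedure, and the treatment is meant to suppress it. If treatment works, NAC reactions should be fewer on active treatment and drug reactions can occur only on active treatment. In a pooled row these two differences pull in opposite directions.

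This matters because protocol 5.2.3 says there are no data on giving the two agents together. A reader looking for systemic reactions to the combination, by grade and arm, would go to the WAO table and could not tell what caused the events in it.

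The unclear place of NAC eye symptoms adds to this. If some of them are graded on the WAO scale, a common and expected challenge response enters the row for systemic reactions.

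**Working it through.** The documents give no rate for WAO-graded reactions, so there is no planned figure to reproduce. The check is mainly a comparison of the texts, followed by an illustration with assumed rates.

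**Step 1. Can any planned table show WAO-graded drug reactions by arm?**

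- Severity within the WAO scale: has grade, lacks trigger.
- Lines for SLIT-related and dupilumab-related events: have trigger, lack WAO grade, and mix systemic with local events. Protocol 1.2.1 puts local mouth reactions at 46-61% in phase 3 trials, so the SLIT line would be mostly local.
- SOC and preferred-term tables by relationship: have trigger and term, lack scale and grade.

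None has both.

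**Step 2. Year 3.** Dosing runs through week 104. Week 104 is Study Day 104 × 7 + 1 = 729; with the 10-day visit window it is 739 at the latest. The Year 3 window in SAP 10.3 opens at Study Day 756. If dosing keeps to schedule, the Year 3 WAO line can hold only procedure reactions, yet nothing in the table says so. This needs no assumed rate.

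**Step 3. Where does a NAC eye symptom go?** Under 12.2.1 it becomes an adverse event only if bothersome and/or treated for more than 2 days. If it qualifies, three routes can be argued:

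- Table 9, as a local reaction, although grades 1 to 3 do not name the eye;
- WAO grade 1, because Appendix 14 lists conjunctival signs and 12.3.1.2 does not exempt them;
- CTCAE under 12.3.1.3, as an event not described elsewhere.

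Table 9 also applies only when there are no systemic signs. If a red eye counts as a WAO sign, a nasal reaction with red eyes could leave Table 9 too. For SLIT, 12.3.1.1 does treat certain expected throat and gastrointestinal symptoms as local, so the silence on NAC eye signs may be an oversight.

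**Step 4. Illustration.** Inputs:

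- 36 participants per arm and three on-study challenges each (Protocol 3.1). The baseline NAC precedes treatment and falls in the screening summary.
- q, the chance per challenge of a qualifying eye event graded on the WAO scale: assumed 1% to 10%.
- d, the true risk of a systemic drug reaction on active treatment: assumed 2% or 5%.
- r, the reduction in NAC events on active treatment: 0 or 30%. The 30% is borrowed from Protocol 1.2, where it refers to the nasal symptom score.

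Share with any WAO event: placebo = 1 − (1 − q)³; active = 1 − (1 − d)(1 − q(1 − r))³.

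Example, q = 3%, d = 2%, r = 30%: placebo = 1 − 0.97³ = 8.7%; active = 1 − 0.98 × 0.979³ = 8.0%; difference −0.7 points against a true +2.

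Difference in the pooled row, active minus placebo, in percentage points:

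| q | d = 2%, r = 30% | d = 5%, r = 30% | d = 2%, r = 0 | d = 5%, r = 0 |
|---|---|---|---|---|
| 1% | +1.1 | +4.0 | +1.9 | +4.9 |
| 3% | −0.7 | +2.1 | +1.8 | +4.6 |
| 5% | −2.3 | +0.4 | +1.7 | +4.3 |
| 10% | −5.9 | −3.5 | +1.5 | +3.6 |

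In events, the between-arm gap from the challenge alone is 36 × 3 × q × 0.30 = 108 × q × 0.30: about 0.3, 0.6 and 1.6 for q = 1%, 2% and 5%. This is an upper figure, because the plan expects 6 participants per arm to miss the year 3 NAC. A table split by trigger would show d itself on the drug lines.

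**The case against.** A reader might infer that the main harm of the drugs is misreported by arm. The documents do not support that. Protocol 5.1.1 calls severe systemic reactions to Grazax rare; the common harm is local and has its own SLIT scale. Events related to SLIT, to dupilumab and to NAC are each reported by arm, overall and by year, so a drug reaction still counts under its drug. Over the whole treatment-emergent period the WAO events are also shown by SOC and preferred term, so an eye term would be visible. All safety data are listed. Serious events and events leading to discontinuation get separate attention, and related grade 3 or higher events trigger the stopping rules in protocol 11.2 and 11.5. All of this stands, and a severe reaction is unlikely to go unseen.

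A reader might also infer that NAC eye symptoms will be graded as systemic and will pile up in double-placebo. That is not established. Protocol 12.3.1.2 sends to the WAO scale only reactions judged systemic. Section 5.4.2 expects eye symptoms yet says a systemic or anaphylactic reaction to NAC has never been seen at the site, so its own usage does not count them as systemic. CTCAE is another route, and the filter in 12.2.1 removes most transient symptoms. This objection also stands: the text is ambiguous, which is a reason to reconcile it but not evidence of misgrading.

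The gap in Steps 1 and 2 survives: no planned table gives WAO grade and drug attribution together.

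**Conclusion.** The WAO table cannot be read as a table of drug reactions, and no other planned table fills that place, although the safety endpoint covers severity and relatedness of systemic events by arm. In Year 3 the row can contain only procedure reactions if dosing ends on schedule.

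The effect on the arm comparison is unknown. It is small if qualifying eye events are rare or equal across arms. Dilution or reversal needs three things together: some eye events graded on the WAO scale, a per-challenge rate of a few percent, and a clear reduction on active treatment. In the illustration with r = 30%, a true 2-point excess changes sign between q = 1% and 3%, and a 5-point excess between 5% and 10%. The values of q and d are assumptions, and r is taken from a symptom score, not from event counts.

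The uncertainty over NAC eye symptoms is a separate, textual point and does not depend on these rates. Overall this is a cheap improvement to the safety tables, not a fault that invalidates the safety reporting.

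**What to change.** (a) Present the WAO-graded table by arm and year, split by recorded attribution: SLIT, dupilumab, NAC and skin testing. Label the drug lines as immediate reactions. First confirm that the skin-testing field covers intradermal tests, because SAP 10.3 lists only the skin prick test. State how events with several attributions are counted, and keep the existing SAP 10.3 rules for missing attribution visible: related for drugs, a separate category for procedures.

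(b) Reconcile protocol 12.2.1, 12.3.1.2 with Table 9, 12.3.1.3 and Appendix 14 on which scale grades NAC eye symptoms that qualify as adverse events. Which scale or grade applies is for the sponsor and the investigator. The note at the end of the SAP shows that the database is locked, so new wording alone would not regrade recorded events; the study report should state which scale was used.

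The cost is one extra split of an existing table and a clarifying statement. No new data are needed if the attribution fields prove adequate. Part (a) also limits the effect of part (b), since eye events attributed to NAC would appear on the NAC line.

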10.4. Deaths, Serious Adverse Events, and Other Significant Adverse Events

Serious adverse events (SAEs) will be listed and summarized in the same manner described above. A separate listing of any death (including time to death and cause of death) as well as a listing of AEs that led to study drug discontinuation will also be created.

10.5. Clinical Laboratory Evaluation

Clinical laboratory measurements include serum chemistry, urinalysis, hematology, and IgE. The IgE collected includes grass pollen specific-IgE, birch pollen specific-IgE, and total IGE. Results will be converted to standardized units where possible.

For numeric laboratory results, descriptive statistics of laboratory values and the change from baseline of laboratory values will be presented for each treatment group. Included in the change from baseline summaries will be the worst post-baseline change from baseline value per parameter/participant. In cases, where the “worst” value can be defined in the low or high direction for a given parameter, both directions will be considered. Note that unscheduled visit results may be considered when deriving the worst value post-baseline.

For categorical laboratory results, the number and percentage of participants reporting each result will be presented for each treatment group.

Data listings will also be provided for clinical laboratory measurements, including the laboratory normal ranges and out-of-range flags to denote abnormal values as high (H) or low (L).

Per the protocol, any abnormal value or result from a clinical or laboratory evaluation may also be entered as an AE and will therefore appear in the AE summary tables.

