APPENDIX 1. SCREENING AND BASELINE ASSESSMENTS

	2020 - 2021			
	Screening	Rescue Medication Dispensing visit	Baseline In Season Assessments	Baseline NAC
Visit	-4	-3 ²	-2	-1
General Assessments				
Informed consent	X			
Demographics	X			
Medical history	X			
Allergy history	X			
Directed physical exam	X			
Rhinoconjunctivitis Severity Screening Evaluation (ARIA severity score)	X			
Vital signs	X			X
Pulmonary Function Testing (FEV1, FVC, PEFR)	X ³			
Adverse events	X	X	X	X
Concomitant medications	X	X	X	X
Local Labs				
Serum pregnancy test				X
Urine pregnancy test	X			X
Hematology	X			X
Comprehensive chemistry	X			X
Total IgE and Specific IgE to grass and birch pollen	X			
Study Medications				
Dispense Rescue medications		X	X	
Clinical Assessments				
Nasal allergen challenge				X
VAS ¹				X
Total nasal symptom score				X
Peak nasal inspiratory flow				X
Peak Expiratory Flow				X
Skin prick test – multiple allergens	X			
Intradermal test - Phleum pratense				X

Rhinitis Assessments				
CSMS ¹			X	
MiniRQLQ ¹			X	
MRSUI			X	
Global Evaluation No. 1				X
Mechanistic Assessments				
PBMCs			X	
Serum FAB antibody assay			X	
Serum pre/8hr post NAC				X
Serum archive			X	
Whole blood flow cytometry (BAT)			X	
DNA methylation			X	
Nasal brushings			X	X
Nasal fluid cytokines			X	X
Whole Blood – RNA in season and pre/ 8hr post NAC			X	X
Whole Blood - DNA (genotyping)			X	

¹ Collected every week during grass pollen season from mid-May to end of July.

² Can be combined with visit -4 for those participants screened after 1 April.

³ May be conducted at any time up until and including visit -1 and/or substituted with Peak Expiratory Flow if required.

APPENDIX 2. SCHEDULE OF EVENTS TREATMENT YEAR 1

	Dosing Year 1																											
Week	0	0	2	4	6	8	10	12	14	16	18	20	22	24	26	28	30	32	34	36	38	40	42	44	46	48	50	52
Visit	0	1	2	3	4	5	6	7	8	9	10	11	12	13	14	15	16	17	18	19	20	21	22	23	24	25	26	27
General Assessments																												
Directed physical exam	X																											
Vital signs	X	X																										
Adverse events ⁷	X	X	X	X	X	X	X	X	X	X	X	X	X	X	X	X	X	X	X	X	X	X	X	X	X	X	X	X
Concomitant medications ⁷	X	X	X	X	X	X	X	X	X	X	X	X	X	X	X	X	X	X	X	X	X	X	X	X	X	X	X	X
Randomization	X																											
Study Medications																												
Dupixent [®] /Dupixent [®] placebo ^{1,2}	X		X	X	X	X	X	X	X	X	X	X	X	X	X	X	X	X	X	X	X	X	X	X	X	X	X	X

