Local Laboratory Assessments																												
Urine pregnancy test ³		X		X		X		X		X		X		X		X		X		X		X		X		X		

¹ Dupixent®/Dupixent® placebo may be administered in-clinic or self-administered as detailed in section 3.1.

² Grazax®/Grazax® placebo taken once daily.

³ To be carried out within 4 weeks prior to any injection. If a visit was missed, this may be completed at an even-numbered visit as needed or performed at home.

APPENDIX 4. SCHEDULE OF EVENTS OBSERVATION YEAR 3

	Observation Year 3												
Week	108 ¹	112 ¹	116 ¹	120 ¹	124 ¹	128 ¹	132 ¹	136 ¹	140 ¹	144 ¹	148 ¹	152 ¹	Un
Visit	54	55	56	57	58	59	60	61	62	63	64	65	Early Term
General Assessments													
Vital signs													X
Directed physical exam													X
Pulmonary Function Testing (FEV1, FVC, PEFR)													X
Adverse events	X	X	X	X	X	X	X	X	X	X	X	X	X
Concomitant medications	X	X	X	X	X	X	X	X	X	X	X	X	X
Pregnancy questionnaire	X	X	X	X	X	X	X	X	X	X	X	X	X
Local Laboratory Assessments													
Hematology													X
Comprehensive chemistry													X
Specific and Total IgE													X

¹ Phone visit.

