APPENDIX 5. SCHEDULE OF EVENTS IN AND OUT OF SEASON

	2022					2023					2024				
	Out of Season	Pre-season	In season	Out of season		Pre-season	In season	Out of season		Pre-Season	In season	Out of season			
Month	Jan-Apr	Apr-May	May-Aug	Sep-Jan	Sep-Feb	Jan-Apr	Apr-May	May-Aug	Sep-Jan	Sep-Feb	Jan-Apr	Apr-May	May-Aug	Sep-Jan	Sep-Feb
Visit	S1	S2	S3	S4	S5	S6	S7	S8	S9	S10	S11	S12	S13	S14	S15
General Assessments															
Directed physical exam						X					X				X
Vital signs				X					X					X	
Pulmonary function testing (spirometry)				X					X					X	
Adverse events	X	X	X	X	X	X	X	X	X	X	X	X	X	X	X
Concomitant medications	X	X	X	X	X	X	X	X	X	X	X	X	X	X	X
Study Medications															
Dispense Rescue Medications		X	X				X	X				X	X		
Clinical Assessments															
Nasal allergen challenge ¹				X					X					X	
VAS	X			X	X	X			X	X	X			X	X

¹ To ensure the NAC is done at the same time each year, the yearly NAC should be performed +/-14 days from the calendar date of the baseline out-of-season NAC (V-1).

	2022					2023					2024				
	Out of Season	Pre-season	In season	Out of season		Pre-season	In season	Out of season		Pre-Season	In season	Out of season			
Month	Jan-Apr	Apr-May	May-Aug	Sep-Jan	Sep-Feb	Jan-Apr	Apr-May	May-Aug	Sep-Jan	Sep-Feb	Jan-Apr	Apr-May	May-Aug	Sep-Jan	Sep-Feb
Visit	S1	S2	S3	S4	S5	S6	S7	S8	S9	S10	S11	S12	S13	S14	S15
Total nasal symptom score				X					X					X	
Peak Expiratory Flow				X					X					X	
Peak nasal inspiratory flow				X					X					X	
Skin prick test endpoint titration - Phleum pratense					X					X					X
Intradermal test- Phleum pratense				X					X					X	
Local Laboratory Assessments															
Hematology			X		X			X		X			X		X
Comprehensive chemistry															X
Urine pregnancy test														X	
Rhinitis Assessments															
CSMS ²			X					X					X		

	2022					2023					2024				
	Out of Season	Pre-season	In season	Out of season		Pre-season	In season	Out of season		Pre-Season	In season	Out of season			
Month	Jan-Apr	Apr-May	May-Aug	Sep-Jan	Sep-Feb	Jan-Apr	Apr-May	May-Aug	Sep-Jan	Sep-Feb	Jan-Apr	Apr-May	May-Aug	Sep-Jan	Sep-Feb
Visit	S1	S2	S3	S4	S5	S6	S7	S8	S9	S10	S11	S12	S13	S14	S15
MiniRQLQ ²			X					X					X		
MRSUI			X		X			X		X			X		X
Global Evaluation No. 1 ³				X					X					X	
Global Evaluation No. 2 ³				X					X					X	
Mechanistic Assessments															
PBMCs			X		X			X		X			X		X
Serum FAB antibody assay			X		X			X		X			X		X
Serum pre/8hr post NAC				X					X					X	

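### The pooled worst post-baseline laboratory summaries in SAP 10.5 do not fit the sampling schedule: no scheduled on-treatment chemistry, no scheduled post-baseline local IgE, and hematology drawn from mixed periods

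*SAP*

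**What the plan says.** SAP 10.5 sets the scope: "Clinical laboratory measurements include serum chemistry, urinalysis, hematology, and IgE". On IgE it adds: "The IgE collected includes grass pollen specific-IgE, birch pollen specific-IgE, and total IGE". For numeric results, "descriptive statistics of laboratory values and the change from baseline of laboratory values will be presented for each treatment group". The next sentence is the one at issue: "Included in the change from baseline summaries will be the worst post-baseline change from baseline value per parameter/participant". Unscheduled samples are left optional: "Note that unscheduled visit results may be considered when deriving the worst value post-baseline". No treatment period is attached to the worst value.

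SAP 8.1 takes as baseline the last value before first treatment. SAP 8.3 ties summaries to the nominal visit. It lets unscheduled and early-withdrawal results be tabulated separately but not stand in for nominal data, except where an early-withdrawal visit overlaps the window of a missed scheduled visit.

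The protocol's schedules are in five appendices:

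- **Appendix 1 (before treatment):** chemistry and hematology at Visits -4 and -1. The row "Total IgE and Specific IgE to grass and birch pollen" is marked at Visit -4 only.
- **Appendices 2 and 3 (weeks 0 to 104):** the only local laboratory test is the urine pregnancy test.
- **Appendix 4 (year 3):** hematology, chemistry and the row "Specific and Total IgE" are marked only in the last column, for unscheduled and early-termination visits.
- **Appendix 5 (seasonal visits):** the row "Comprehensive chemistry" has one mark, at S15. Hematology is marked at S3, S5, S8, S10, S13 and S15. There is no IgE row.

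**The concern.** A worst post-baseline table by arm is normally read as a summary of what happened under treatment. Here that reading would be wrong for chemistry. For a completer with no unscheduled visit, the worst value is simply the S15 value, taken many months after the last dose. In the same column it would sit beside values from other participants that were triggered by an event or by leaving the study, some of them on treatment.

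For local IgE, change by arm would come from a few participants selected after randomisation. Their number and reasons for being sampled can differ between arms. For hematology, a year-3 sample can supply the worst value, although eosinophilia is a listed dupilumab reaction (Protocol Tables 4 and 5) and the on-treatment period is the one of interest.

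This matters because Protocol 5.2.3 says there are no human data on giving the two products together, and Protocol 2.4 makes safety and tolerability a secondary objective. SAP 10.3 divides adverse events into years 1, 2 and 3. The worst laboratory values get no such division.

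**Working it through.** **Step 1. Scheduled post-baseline samples, counted from Appendices 2 to 5.**

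| Parameter | Treatment period | Around week 104 | Year 3 | Total |
|---|---|---|---|---|
| Chemistry | 0 | 0 | 1 (S15) | 1 |
| Local IgE | 0 | 0 | 0 | 0 |
| Hematology | 3 (S3, S5, S8) | 1 (S10) | 2 (S13, S15) | 6 |

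**Step 2. Can S15 fall on treatment?** Inputs are the windows in Protocol 8.5. Measure days from Visit -1 and define:

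- g = days beyond the 28-day minimum to Visit 0
- e = deviation of the annual challenge from its anniversary (-14 to +14)
- h = days beyond the 28-day minimum from the challenge to S15 (or S10)

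Then:

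- Week-104 dose = 28 + g + 728
- S15 = 1096 + e + 28 + h (three calendar years including 29 February 2024)
- S15 minus dose = 368 + e + h - g

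The smallest gap takes Visit -1 on 1 September 2021 and Visit 0 on 28 February 2022, which are 180 days apart, so g = 180 - 28 = 152. Put e = -14 and h = 0, and let the last dose run 10 days late: 368 - 14 + 0 - 152 - 10 = **192 days**. By dates, this is 7 March 2024 to 15 September 2024. It is a floor. If S14 may not fall before 1 September, as the month window implies, the gap is 192 + 14 = 206 days. S15 chemistry is off-treatment for anyone following the schedule.

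**Step 3. Where do the hematology samples fall?**

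- S3 and S5 precede the planned end of treatment by construction. S8 ends in August 2023. The earliest Visit 0 is 29 September 2021, so the earliest week-104 visit is 27 September 2023 less 10 days, 17 September 2023. S8 is therefore within the planned treatment period.
- S13 starts in May 2024. The latest week-104 dose is 7 March 2024, at least 55 days before. S13 is off-treatment.
- S10 is one year before S15, and two calendar years from Visit -1 are 730 days. S10 minus dose = 730 + 28 + e + h - (28 + g + 728) = 2 + e + h - g. At one extreme this is 2 - 14 + 0 - 152 - 10 = -174 days. At the other, Visit -1 is on 1 September 2021, g = 0, S10 is on 29 February 2024 (e + h = 181 - 28 = 153) and the dose is 10 days early: 2 + 153 + 10 = +165 days. S10 therefore straddles the last dose. The off-treatment count among the six is 2 or 3, depending on the participant.

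**Step 4. How many participants could supply IgE change?** Protocol 13.6 plans for 6 of 36 per arm without the year-3 challenge. This reproduces its own total: 90 / (1 - 6/36) = 108. If all six attended the invited exit visit (Protocol 11.4) and nobody else had an unscheduled sample, about 6 of 36 per arm would have a post-baseline IgE. This is an illustration, not a limit.

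**Step 5. Which tables does this touch?** Under SAP 8.3, by-visit change tables show S15 chemistry as S15, and the S3 and S8 hematology samples apart from S13 and S15. IgE has no nominal post-baseline visit to show. The pooling occurs only in the worst-value derivation. Because unscheduled results only may be considered there, the IgE worst-change table is either empty or made up of selected participants, depending on a choice the SAP leaves open.

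A side observation: SAP 10.5 also lists urinalysis, for which the protocol schedules nothing beyond urine pregnancy tests.

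**The case against.** The strongest reply is that these tables are descriptive. The safety endpoint in Protocol 3.3 is adverse events. Abnormal laboratory results can be recorded as adverse events, and SAP 10.3 tabulates those by year. Neither document says chemistry will be used to claim on-treatment safety. Local IgE serves mainly for eligibility, and serum IgE may be measured under the separate mechanistic plan. Sparse IgE counts would be visible in any table. All of this stands, and it limits the weight of the point. It does not make the pooled worst value interpretable.

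Four stronger readings are tempting, and the documents do not support them:

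- **That no laboratory change table distinguishes period.** SAP 8.3 keeps ordinary tables by nominal visit.
- **That post-baseline IgE and on-treatment chemistry come only from dropouts.** Protocol 8.4 allows unscheduled visits for adverse events or exacerbations, and SAP 10.5 allows those results to count. Participants who stay in the study can therefore contribute.
- **That at most 6 of 36 per arm could have such values.** The 16.6% is a planning assumption about the year-3 challenge. The exit visit is by invitation, and participants who stop treatment are asked to remain in follow-up, so the number could be lower or higher.
- **That exactly two of six hematology samples are off-treatment, so a cut at the last dose date solves the problem.** S10 falls on either side of that dose through scheduling, and a strict cut would divide it by chance.

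**Conclusion.** The point holds for the pooled worst post-baseline summaries and for IgE change by arm. As scheduled, chemistry offers no sample in 104 weeks of treatment and one sample at least 192 days after the planned last dose. Local IgE offers no post-baseline sample. Hematology offers three samples on treatment, one around its end and two in year 3. One worst value per participant over all of these does not describe a single period, and for IgE it does not describe a randomised comparison.

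The effect is confined to descriptive laboratory displays. It changes no efficacy endpoint, test or stopping rule. A reader might infer that the trial's safety conclusion is unsound, but the documents do not support that, because adverse events are collected throughout and reported by year.

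The result rests on reading the schedule marks by column from extracted tables, where neighbouring rows align consistently, and on visits following the Protocol 8.5 windows. The actual number of unscheduled and early-termination samples is unknown.

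**What to change.** In SAP 10.5:

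1. **IgE:** list local IgE collected after screening, and drop its change and worst-change summaries by arm.
2. **Chemistry:** present S15 as an off-treatment result. Keep unscheduled and early-termination values separate from it. Add a footnote that no on-treatment chemistry was scheduled.
3. **Hematology:** derive the worst value separately for the treatment period (S3, S5, S8, S10 and unscheduled samples in that period) and for year 3 (S13, S15 and later unscheduled samples). Assign S10 by nominal visit rather than by a strict last-dose cut, and footnote that it falls around the last dose. Show samples taken after early treatment discontinuation separately.

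No new sample or visit is involved. The cost is SAP wording, a small amount of table programming, and a laboratory safety statement slightly less favourable than the pooled table would suggest. The note attached to the SAP was written after database lock, so the change may have to be made in the report tables and footnotes, recorded as a departure from the SAP.
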